# 1.0 Objectives / Specific Aims

Via a successfully completed Phase I STTR, our investigative team developed and preliminarily clinically evaluated Moodivate, a self-help mobile app informed by Brief BA to be utilized for depression treatment among adult primary care patients. Results of our Phase I study indicate that Moodivate is feasible and acceptable to primary care patients and that use of the app relative to TAU is associated with significantly greater decreases in depressive symptoms over time. This Phase II STTR will allow us to refine, improve, and rigorously evaluate Moodivate.

Aim 1: Refine Moodivate and develop the EHR provider portal (months 1-12). Iterative usability testing with patients (n=10) and providers (n=10) will be utilized to refine both the app and the portal. Milestones: 1) Development of a HIPAA-compliant Moodivate EHR portal, 2) Android expansion of Moodivate, and 3) completed app modifications consistent with feedback from Phase I participants.

Aim 2: Via a three-arm randomized controlled trial (N=695), examine the efficacy of 1) Moodivate vs. 2) Moodivate + EHR integration vs. 3) treatment as usual (TAU) for the treatment of depressive symptoms within primary care (months 12-30). Main outcomes include: 1) change in depression over time as a function of treatment and 2) patient- and provider-level treatment feasibility and acceptability. Milestones: 1) Determination of clinical efficacy of Moodivate and Moodivate + EHR relative to standard practice for depression treatment and 2) demonstrated treatment acceptability and feasibility, defined as  $\geq$ 70% app retention across follow-up and patient and physician self-reported benefit of utilizing Moodivate.

Aim 3: Conduct a cost-effectiveness analysis of implementing Moodivate and Moodivate + EHR integration within primary care practices relative to TAU (months 30-36).

Milestones: Derivation of incremental cost-effectiveness of Moodivate and Moodivate + EHR vs. TAU.

# 2.0 Background

**Depression is a Major Public Health Problem and the Leading Cause of Disability Worldwide.** Depression is the leading cause of disability worldwide, with more than 300 million people affected . In the United States alone, 16.2 million adults report a past year major depressive episode (MDE) and an additional 38 million experience subsyndromal depression. Individuals with depressive symptomatology experience significant suffering, high morbidity and mortality, and considerable social and occupational impairment. As such, efficient and effective identification and treatment of depression is of critical public health importance.

**Primary Care Offers a Ripe Opportunity for Depression Treatment.** Most adults with depressive symptoms make at least one annual medical visit to a primary care physician (PCP). Thus, primary care offers a ripe opportunity to identify and treat adults with depressive symptoms. This is consistent with guidelines from the United States Preventive Services Task Force, which specify that depression screening should be implemented in the general adult primary care population with systems in place to ensure appropriate diagnosis, treatment, and follow-up. Despite these recommendations, depression has historically been undertreated in primary care and **more than two-thirds of U.S. adults who screen positive for depression do not receive treatment**. Lack of depression treatment via primary care results in negative outcomes for patients, including prolonged depressive episodes, decreased recovery incidence, and heightened impairment and suffering.

Table 1: Current Primary Care Psychotherapy Market

Evidence-based depression treatments that can be delivered via primary care medications include antidepressants) and psychotherapy. Although primary care patients with depressive symptoms tend to prefer psychotherapy, the vast majority (87%) of patients treated are prescribed medications without therapy offered even as an option. Of the 21.2 million U.S. adults who visit a PCP annually and screen positive for depression, only 6.6% receive therapy  $(Table 1)^2$ . One key barrier is limited access to mental health specialty care. Within one nationally representative

U.S. adults	327.2
	million
U.S. adults who visit a PCP $\geq 1x/year$	251.9
	million
U.S. adults who visit a PCP $\geq 1x/year$ and	21.2 million
screen + for depression	
U.S. adults who visit a PCP $\geq 1x/year$ , screen +	6.1 million
for depression, and receive treatment	
U.S. adults who visit a PCP $\geq 1x/year$ , screen +	5.3 million
for depression, and receive antidepressants	
U.S. Adults who visit a PCP $\geq$ 1x/year, screen +	1.4 million
for depression, and receive psychotherapy	
Current untapped market for psychotherapy	19.8 million
via primary care within the U.S.	

survey, 66.8% of PCPs reported they were unable to get high-quality outpatient mental health services for their patients. From a patient perspective, therapy barriers include problems of transportation, childcare, lack of time, stigma, and lack of available services. There is clear need for a disseminable, evidence-based psychotherapy treatment option to meet the need for depression treatment via primary care. Such a product would not only address a public health need but would also be commercially viable.

Mobile Health Technologies can be Leveraged to Deliver Evidence-Based Depression Treatment via Primary Care. Mobile health (mHealth) technologies offer an ideal strategy to meet the need for evidence-based psychological depression treatment via primary care. Several computerized psychological interventions for depression treatment via primary care have previously been developed and have demonstrated success . However, mobile technologies, such as smartphones and mobile apps may be superior treatment delivery platforms as they allow continuous, patient-driven access to treatment materials while also eliminating barriers to computerized treatment (e.g. the need to have a computer at home or go to a clinic to access the treatment). Smartphone ownership in the U.S. has grown year over year and now 77% of adults own smartphones, with high smartphone ownership rates across age groups—92% of Millennials, 85% of Gen Xers, and 67% of Baby Boomers own smartphones. Moreover, the majority of physicians report utilizing mobile apps in their clinical practices. Thus, treatment access barriers could be reduced if evidence-based psychotherapy could be efficaciously delivered via smartphone. Apps delivered directly within primary care settings could provide an immediately actionable, evidence-based treatment for patients in need of services for depressive symptoms.

[figure not shown]
Brief Behavioral Activation is an Evidence-Based Depression Treatment Well-Suited for mHealth Delivery via Primary Care. To be an attractive treatment option for PCPs to recommend to their patients, a mobile app-based depression treatment must be strongly grounded in evidence-based treatment and have a research base supporting primary care implementation. Among evidence-based depression psychotherapies, brief Behavioral Activation Treatment for Depression (Brief BA) has shown great promise and is particularly amenable to mHealth delivery within primary care. Brief BA is grounded in behavioral principles, which suggest that depression is caused by a lack of reinforcement in the environment for positive, non-depressed behaviors. Thus, the goal of Brief BA is to help the patient identify, schedule and reengage in positive activities. Brief BA accomplishes this via the following components, delivered across five to ten sessions: 1) Psychoeducation: Introduction to the Brief BA model; 2) Identification of life areas, values, and associated activities: Identification of values and goals within a variety of life areas important to the patient, including relationships, education, career, recreation, and health; 3) Daily monitoring and activity planning: Selection of activities that allow the patient to live according to his/her

values and incorporation of the activities into the patient's daily schedule; and 4) Contracts: Identification of a supportive individual to facilitate completion of difficult activities.

Brief BA was originally developed by [name] (study consultant) and colleagues in 2001 and several large-scale randomized controlled trials (RCTs) since that time have demonstrated the efficacy and cost-effectiveness of the treatment for depressive symptoms. Across studies, Brief BA is associated with reductions in depressive symptoms including among those with Major Depressive Disorder (MDD). Brief BA treatments have been delivered successfully within primary care clinics both by mental health nurses and psychologists. Further, Brief BA has shown promise in a variety of other health care settings, including oncology, the Veteran's Administration health system^33, and substance use treatment. Across studies, effect size estimates for Brief BA are in the medium to large range indicating meaningful clinical impact. A key strength of Brief BA that makes it fitting for mobile app delivery is that it is simple, straightforward, and easily understood by patients.

**Progress Report.** The overarching goal of our Phase I STTR was to tailor the delivery of Brief BA for mHealth within primary care. We developed "Moodivate," a self-help patient-facing mobile app informed by Brief BA (**Figure 1**). Moodivate development began with a diverse team of PCPs, psychologists, and app developers (all investigators herein) to ensure psychological treatment components were faithfully translated to a mobile platform in a manner fitting the primary care environment. We utilized an agile development approach, which promotes continued collaboration across the software development lifecycle between the entire team^40.

Figure 1: Moodivate Screenshots

When users first download Moodivate, they complete a psychoeducational interactive tutorial illustrating the connection between thoughts, feelings, and behavior. This tutorial highlights that Moodivate will focus on increasing activity to improve mood and decrease the incidence of negative thoughts (*Figure 1*). Users practice generating values and activities and receive instruction regarding app use. Users are then taken to the "Life Areas" screen, where they select from five life areas (Relationships, Daily Responsibilities, Recreation, Career and Education, Health) to develop values. A value is defined as an ideal, quality, or belief in a certain way of living. For example, within the relationships life area, a user might generate a value of "Be a trustworthy friend." This value-driven framework ensures that activities will be positively reinforced over time, by virtue of being connected to what the user values as important. Users generate several values within each life area. Values are then used as a framework to generate activities. For the user who generated the value of "Be a trustworthy friend", activities might include going to dinner with a friend once a week or calling a friend for 20 minutes twice a week. Users generate several activities for each value.

Once a user has generated activities across values, activities are scheduled and monitored via the Calendar. After completing an activity, the user receives reinforcement (e.g., "Nice going, you did it!"). Sometimes activities are difficult to complete individually and require help from others. For example, a user might schedule an activity to grocery shop weekly but might not have transportation. In these instances, users can enlist social support via the "Assists" screen through which they identify an individual who could help them

complete the scheduled activity and schedule a time to ask that individual for help. Moodivate users can track daily mood to monitor progress. Calendar prompts remind users to rate their mood each day. Users can view a graph of fluctuations in mood overlaid upon a graph of the number of completed activities, illustrating the

**Table 2: Phase I STTR Participant Demographics** 

	All (N=52)	Moodivate (n=24)	MoodKit (n=19)	TAU (n=9)
Age (M(SD))	43.8(13.3)	44.7(14.0)	43.0(13.6)	43.1(11.9)
Gender (% Female)	84.6%	83.3%	78.9%	84.6%
Race (% White)	40.4%	41.7%	36.8%	44.4%
Ethnicity (%	3.8%	0.0%	10.5%	0.0%
Hispanic)				
Education ( $\% \ge HS$ )	84.6%	91.6%	78.9%	77.8%
Income (% <\$50k)	61.5%	54.1%	68.4%	66.6%

connection between activity and mood. Moodivate users are reinforced for treatment engagement via badges. When a user earns a badge, a pop-up displays and congratulates the user while explaining why the badge was earned. Users can view earned badges on the User Info page.

To examine the feasibility and preliminary efficacy of Moodivate for depression treatment within primary care, we conducted a pilot randomized feasibility trial as part of our Phase I STTR^42. Participants (N = 52); **Table 2**) were recruited from one primary care clinic affiliated with the Medical University of South Carolina (MUSC) and were randomized 2:2:1 to receive: 1) Moodivate, 2) an active control Cognitive Behavioral Therapy mobile app ("MoodKit"), or 3) Treatment As Usual (TAU; no app). Because clinical data are limited on other available mobile apps that purport to treat depression, at the suggestion of NIH program staff, we opted to include the active control comparator (MoodKit) to extend the literature on efficacy data for other clinical apps. Participants completed assessments of depressive symptoms weekly for eight weeks. App analytics data were captured to examine Moodivate feasibility (similar analytics data not available for MoodKit as it was not developed by our team). Moodivate participants on average had 46.8(SD = 30.1) app sessions throughout the trial duration, spent 3.5(2.8) minutes using the app per session, and spent 120.8(101.0) minutes using the app in total throughout the trial. Participants on average generated 6.1(3.2) unique values, 14.7(10.2) unique activities, and completed 52.2(89.3) activities. Nearly 70% of Moodivate participants continued to use the app one month after trial enrollment and 50% at the end of the eight-week follow-up period. A generalized estimating equation (GEE) model examining change in depressive symptoms over time by treatment indicated a significant interaction between time and treatment  $(\gamma^2=42.21, df=14, p<.001)$ . As compared to TAU. Moodivate participants evidenced significantly greater decreases in depression over time. Moreover, these gains were sustained across the trial period. Moodivate participants had an average(SD) 12.2(13.2) point decrease on the Beck Depression Inventory-II (BDI-II; a 10-point decrease is clinically significant) from pre- to post-treatment. At study end, 52.6% of Moodivate participants (vs. 25.0% of TAU) had less than minimal symptoms of depression. Differences between the two app conditions were nonsignificant, as might be expected from a pilot feasibility study not powered to detect small effects. In sum, this trial demonstrated that: 1) our team can feasibly recruit patients with depressive symptoms from primary care, 2) participants randomized to Moodivate utilized the app regularly throughout an eight-week period, and 3) Moodivate use was associated with clinically significant decreases in depression over time relative to TAU.

To Enhance Commercialization, Moodivate Must Be Refined, Expanded, and Further Evaluated. Although these preliminary data are promising, several key issues must be resolved before Moodivate can

be commercialized. First, the patient is not the only customer. Providers and healthcare systems can benefit from more effective, efficient depression treatment. To systematically deliver Moodivate to all patients with depressive symptoms and provide comprehensive follow-up. Moodivate must be integrated with the healthcare system (i.e., with the Electronic Health Record (EHR)) in a manner that will facilitate provider referral and treatment monitoring. Prior studies of such EHR integration for the management of other chronic diseases including diabetes and obesity indicate that integration of patient data captured via consumer technologies with the EHR facilitates more efficient workflow, improves patient-provider communication, and ultimately improves efficacy. Herein, we will integrate the patient-facing Moodivate mobile app with the EHR. This integration will be developed in partnership with PCPs to reduce workflow burden and promote feasibility and acceptability. Via the Moodivate EHR portal, providers will be able to track their patient's Moodivate treatment utilization and response. This portal could also be used to provide additional support to patients not adherent to Moodivate, to reinforce those using the app and responding, and to track clinical outcomes across patients at the provider- and clinic-levels. Beyond potential patient-level benefits of Moodivate (i.e., improved health), systems-level integration of Moodivate with the EHR will allow clinics and health-care systems to improve rates of depression treatment, a key metric for Accountable Care Organizations (ACOs) from the Centers for Medicare and Medicaid Services (CMS). Reimbursements for ACOs by CMS are directly linked to the percent of adult patients screened and treated for depression. As such, Moodivate integrated with the EHR could help rapidly disseminate depression treatment to patients who screen positive and subsequently increase reimbursement rates.

Second, our experience shows that minor product modifications are needed prior to additional clinical evaluation and commercialization. In Phase I, we developed Moodivate for iOS only to rapidly develop and test a minimum viable product (MVP). During our Phase I trial. we found that 56% of primary care patients enrolled were Android owners. For purpose of the trial, these individuals were allowed to borrow a study iPhone to use throughout the trial. However,

Table 3: Suggested App Refinements as a Result of Phase I

App Feature	Participant Suggestion
Assists	"It was difficult to understand what I was supposed
	to do with the Assist."
Activities	"It might be nice to have a bank of activities and
	values. It was hard to come up with things I wanted to
	do. Like be a better friend, I had that value, and having
	suggested activities would have been helpful."
Calendar	"I would like to get reminders to do things 15
	minutes before I scheduled an activity to occur."
Mood Rating	"When I rate my mood low, it would be helpful to
	offer suggestions of activities I completed in the
	past that helped improve my mood. When you're
	feeling down it's difficult to think of what to do to feel
	better."

to commercialize Moodivate, the app must be expanded to Android. Additionally, as part of Phase I, participants randomized to Moodivate completed a qualitative interview at study end to identify modifications that would promote engagement (*Table 3*). These refinements cluster around: 1) improving the Assists component, 2) incorporating tailored suggestions for values and activities, 3) developing notifications for when activities are scheduled, and 4) offering tailored support when users record low mood.

Third, in Phase I we primarily focused on the feasibility and acceptability of Moodivate. To advance toward commercialization and collect data that may be necessary for the FDA regulatory path, a larger-scale clinical trial is needed in which the efficacy and safety of Moodivate are comprehensively evaluated.

Fourth, any downstream commercialization of Moodivate within healthcare systems requires that we first quantify its cost-effectiveness, both as a stand-alone app and as integrated with the EHR. Via our clinical trial and subsequent cost-effectiveness analyses we will determine: 1) whether there is added clinical benefit of Moodivate EHR integration and 2) the incremental cost of any added clinical benefit from a) Moodivate

+ EHR integration vs. sole provision of Moodivate, b) Moodivate + EHR integration vs. TAU, and c) Moodivate vs. TAU.

Summary of Scientific Premise and Potential to Lead to a Marketable Product. Via a successfully completed Phase I STTR, our investigative team developed and preliminarily clinically evaluated Moodivate, a self-help mobile app informed by Brief BA to be utilized for depression treatment among adult primary care patients. Results of our Phase I study indicate that Moodivate is feasible and acceptable to primary care patients and that use of the app relative to TAU is associated with significantly greater decreases in depressive symptoms over time. This Phase II STTR will allow us to refine, improve, and rigorously evaluate Moodivate. Activities proposed via Phase II will move us toward Phase III and commercialization. Outcomes of this Phase II clinical trial will position us well in the current movement across healthcare in which traditional care delivery is being replaced with patient-centric care, facilitated by digital health tools. This Phase II STTR is wholly consistent with PA-18-579 (Complex Technologies and Therapeutics Development for Mental Health Research and Practice) as well as with NIMH's strategic priorities to "support development, refinement, and implementation of evidence-supported digital health technology into routine practice." Most importantly, commercialization of Moodivate will help to address the public health need for psychological depression treatment via primary care.

#### 3.0 Intervention to be studied

Moodivate. Details of Moodivate are provided in the "Progress Report" section above. Participants randomized to the Moodivate condition will be instructed to utilize Moodivate regularly, at least once per day, for the treatment of depressed mood.

Moodivate + EHR Provider Portal. Participants randomized to the Moodivate + EHR condition will receive similar instructions as those randomized to Moodivate, but will also be instructed that their PCP will have access to metrics related to their app utilization and may choose to follow-up with them regarding treatment utilization and response. The PCP for each participant randomized to this condition will be provided EHR access to Moodivate metrics. Portal design will be developed iteratively with providers as part of Aim 1, but we expect that it will include metrics related to change in mood, frequency of app utilization, and frequency of activity completion.

TAU. TAU is designed to mimic existing standard treatment for depression. Participants in all conditions, including TAU, will be provided educational material about mood management available via the EHR with the suggestion to discuss questions with their PCP. Across conditions, participants will not be precluded from obtaining additional treatment (medication or psychotherapy), which will be tracked as a study outcome.

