#### **Assessment Grids**

Questionnaires	Screening	Final Eligibility	Baseline	Week 1	Week 2	Week 3	Week 4	Week 5	Week 6	Week 7	Week 8	Week 12
Screening Questionnaire	X											
PHQ-9	X	X		X	X	X	X	X	X	X	X	X
BDI-II		Х		Х	X	Х	Х	Х	X	Х	Х	х
App Utilization Questionnaire (Analytics data)				х	х	х	х	х	х	х	х	х
Moodivate Usability Survey (Feasibility/ Acceptability)				х	х	х	х	х	х	х	х	х
System Usability Scale				X			X				Х	Х
Patient Satisfaction Scale			х									х
Current Use of Psychotropic Meds			X				Х					Х
SHAPS			Х				X					х
EROS			X				х					X
BADS			х				х					х

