### 8.0 Recruitment Methods

We will utilize proactive recruitment prior to primary care visits to give patients time to utilize their assigned treatment prior to their next primary care visit. For those randomized to Moodivate + EHR, proactive recruitment will ensure there is data available within the EHR for the PCP to review. Our team has previously implemented similar proactive recruitment approaches with success, utilizing EHR fields to identify intended patient populations. Herein, we will utilize available EHR data to identify Primary Care ICCE patients with depressive symptoms. As part of routine clinical care, all patients complete the Patient Health Questionnaire-2 (PHQ-2) to screen for depression during each primary care visit. Because all participants will be current Primary Care ICCE patients, they will all have completed the PHQ-2 during their last primary care visit. Information on depression is also available via the EHR within each patient's problem list and billing codes. Adult (age 18+) patients will be identified who have an upcoming visit scheduled within the next four weeks and have either: 1) a score of > 3 on their last PHQ-2 assessment (the optimal cut-point to identify those symptomatic), 2) depression listed on their problem list, or 3) a depression-related billing code associated with their last visit. In the last year alone, 6,102 patients have been treated via Primary Care ICCE clinics that would meet these enrollment **criteria.** With the permission of their PCP, these patients will be contacted by the study team via the patient EHR portal (MyChart) with an invitation to participate in the study. If participants do not respond to this invitation within 72-hours, we will contact them via phone, e-mail, and/or text-message (based on preferences within the EHR) to ensure they received the message. We currently implement this recruitment approach in an ongoing trial of an electronic visit for smoking cessation, and our experience has been that it is feasible and efficient to generate a recruitment report via the EHR and that all PCPs associated with the MUSC Primary Care ICCE have agreed to have their patients contacted for the purpose of our studies. If interested, participants will complete an eligibility screening via MyChart/REDCap. This eligibility screening will assess: age, sex, e-mail access, MyChart enrollment, English fluency, smartphone ownership, willingness to use a mobile app for the treatment of depressed mood, and depressive symptoms via the PHQ-9. This eligibility screening will be used solely for screening purposes, not for research purposes. Within our informed consent documents, if a participant provides informed consent to participate in the study, they will agree that their screening information can

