# Aim 2: RCT of Moodivate vs. Moodivate + EHR Provider Portal vs. TAU within Primary Care. Procedures

After completing determination of eligibility and consent, the participant will complete baseline assessments remotely and be randomized via REDCap 1:1:1 to Moodivate, Moodivate + EHR, or TAU. Participants will be randomized via a mixed block design stratified by baseline depressive symptoms and concurrent depression treatment. If randomized to either of the Moodivate conditions, study staff will provide the participant with an app download code and will ensure successful download. Study staff will then give the participant a brief, scripted overview (as utilized in our Phase I trial) regarding app utilization and will provide the participant with 10 minutes to use the app and ask questions. Participants randomized to the Moodivate + EHR condition will be told that their PCP will be provided information regarding their Moodivate utilization and may discuss use and response during their next visit. Providers of Moodivate + EHR patients will be granted access to the EHR provider portal **for those patients** and it will be suggested that they review the portal during the patient's next visit. The provider portal will be developed such that it is available for providers to view only if the patient is randomized to the Moodivate + EHR condition.

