The economic evaluation of Moodivate and Moodivate + EHR relative to TAU will be conducted from the budgetary perspective, as the primary focus herein is on the financial attractiveness of Moodivate for commercial launch. Health systems and payors in particular may be more likely to adopt Moodivate if it is established as either 1) cost-saving or 2) providing a clinical benefit cost-effectively. To examine cost-saving, we will first conduct a cost-benefit analysis by comparing changes in BDI-II scores and any reduction in all-cause and mental health-related healthcare expenditures for a 12-month period before and after Moodivate implementation (or Moodivate + EHR) relative to TAU. Cost data for all inpatient, outpatient and emergency department (ED) care will be obtained from the MUSC primary care ICCE billings department. As study participants may seek care outside of the MUSC system, we will also obtain all-payors' claims data from South Carolina's Revenue and Fiscal Affairs Office (RFA). RFA maintains data on inpatient and ED utilization across the state regardless of patients' point of care. The case for Moodivate (with or without EHR) adoption and commercialization will be the strongest if the product reduces healthcare expenditures while also improving depressive symptoms.

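### Psychotherapy is declared a tracked outcome, but the schedule collects only medication, and the concurrent-treatment stratum is left undefined

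*Combined protocol and SAP*

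**What the plan says.** Section 3.0, under TAU, applies to all conditions: "participants will not be precluded from obtaining additional treatment (medication or psychotherapy), which will be tracked as a study outcome". Both kinds of treatment are named.

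The participant grid in Section 4.0 has one row on such treatment, "Current Use of Psychotropic Meds", marked at Baseline, Week 4 and Week 12. There is no row for psychotherapy or counselling.

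Section 10.0 (Aim 2, Procedures) states: "Participants will be randomized via a mixed block design stratified by baseline depressive symptoms and concurrent depression treatment". The second factor is not defined, and its data source is not given.

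For Aim 3, Section 11.0 plans two sources of cost data. The first is local: "Cost data for all inpatient, outpatient and emergency department (ED) care will be obtained from the MUSC primary care ICCE billings department". The second is state claims data, described as follows: "RFA maintains data on inpatient and ED utilization across the state".

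**The concern.** The protocol promises to track two kinds of additional treatment and schedules a measure for one. The missing one is the closer to the intervention, because the app is itself built on a psychotherapy.

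The trial also gives reasons to expect therapy use to change during follow-up, possibly unequally. Section 13.0 provides that participants who deteriorate receive referrals and are advised to seek treatment, and may stay in the trial. In the Moodivate + EHR arm, the primary care provider sees app metrics and is encouraged to review them at the next visit, which could prompt a referral. Participants know whether they have been given the app. If therapy use differs by arm and is not recorded, the report cannot say what usual care consisted of, or how much psychotherapy accompanied each arm's result.

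The same gap touches randomization. A factor based on concurrent depression treatment needs a definition and a data item that is available before allocation.

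**Working it through.** No sample size, power or alpha figure depends on this point, so the main check is textual. The arithmetic only indicates scale.

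**Step 1. Look for a psychotherapy measure wherever one could be.**

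- Section 4.0, endpoints: the heading on treatment utilization refers to app and portal analytics. The heading on depression treatment practices is a provider questionnaire. Additional treatment is not listed.
- Section 4.0, participant grid: medication only.
- Section 8.0, eligibility screening: "This eligibility screening will assess: age, sex, e-mail access, MyChart enrollment, English fluency, smartphone ownership, willingness to use a mobile app", followed by the PHQ-9. Current treatment is not in the list.
- Section 11.0, Aim 2 analysis: no analysis of medication or psychotherapy use.
- Sections 10.0 and 11.0, Aim 3: MUSC billings include outpatient care, so some in-system therapy may be visible. The state data are described in terms of inpatient and ED use. Neither source is named as the measure of additional treatment, and neither is described as covering outpatient therapy outside MUSC.

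**Step 2. Check whether the stratum can be filled.** The only scheduled item that could inform it is the medication row at Baseline. Section 10.0 puts Baseline first: "the participant will complete baseline assessments remotely and be randomized via REDCap 1:1:1". Section 13.0 (Protections Against Risk) lists randomization before baseline assessments. On that second order, even the medication item would not be available at allocation.

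**Step 3. Scale, from Table 1 in Section 2.0** (millions of U.S. adults who see a PCP at least yearly and screen positive): all 21.2; treated 6.1; antidepressants 5.3; psychotherapy 1.4.

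- Reproducing the plan's own percentages: 1.4 / 21.2 = 6.6% receive therapy, and 5.3 / 6.1 = 87% of those treated receive antidepressants. Both match the text of Section 2.0.
- Psychotherapy among treated patients: 1.4 / 6.1 = 23%. This is the share whose therapy a medication-only form would not record.
- Therapy without an antidepressant, upper limit: 6.1 − 5.3 = 0.8, and 0.8 / 6.1 = 13% of treated patients. As a share of all who screen positive, 0.8 / 21.2 = 3.8%.
- Lower limit: 0%, if everyone in therapy also takes an antidepressant.

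Only patients in therapy without medication would be wrongly placed in an untreated stratum by a medication item, so the range for misplacement is 0% to 13% of treated patients. The form asks about psychotropic medication, which is broader than antidepressants, so 13% is an upper limit.

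**The case against.** The strongest reply is that the gap is smaller than it looks and sits away from the primary result. Additional treatment is not among the Section 4.0 endpoints and has no planned analysis. MUSC billing will include outpatient care, with mental health-related spending over 12 months before and after implementation, so part of the therapy use may be recoverable. This stands as a limit on the point. It does not remove it: these are cost data not assigned to this outcome, and they would miss outpatient therapy delivered elsewhere.

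Four stronger readings are tempting, and the documents do not support them.

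- A reader might infer that the outcome cannot be derived at all, for any of the 695 participants. Billing may give partial capture, so the supportable statement is incomplete capture with no named source.
- A reader might infer that the stratum is set on medication alone. Section 10.0 says neither that nor that psychotherapy is included. It leaves the factor undefined.
- A reader might take 23% as the share placed in the wrong stratum. That figure is therapy use among treated patients, many of whom also take medication; the limit for misplacement is 13%.
- A reader might object that outside therapy cannot be adjusted for. Therapy started after randomization is permitted in every arm and is part of what is being compared. Adjusting for it could introduce bias, so only the loss of description by arm counts.

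**Conclusion.** The mismatch is real: Section 3.0 commits to tracking psychotherapy in all arms, and nothing in the schedule measures it. Followed as written, the plan would leave that half of a declared outcome only partly recoverable, from a source not designated for it, and self-reported therapy use cannot be reliably reconstructed later.

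The consequences are moderate. Co-treatment could not be fully described by arm, which limits interpretation of the comparisons with TAU. A misassigned stratum would slightly weaken balance on that factor. Because the error precedes allocation, it would not bias the treatment comparison, and it should not be read as a threat to the primary test.

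The 23% and the 0% to 13% rest on the assumption that trial patients resemble the national population in Table 1. They may not: eligibility requires scores of at least 10 on both the PHQ-9 and the BDI-II, and willingness to use an app. The point about the stratum also rests on reading concurrent depression treatment as covering both kinds, which is how Sections 2.0 and 3.0 use the idea. If medication alone is meant, the text should say so.

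**What to change.** 1. Add a psychotherapy item to the existing medication form at Baseline, Week 4 and Week 12: currently receiving it (yes/no), and number of sessions since the last assessment.
2. Define concurrent depression treatment for stratification as medication or psychotherapy, name the item that supplies it, and require that it be collected before randomization. Reconcile the order of baseline and randomization between Section 10.0 and Section 13.0.
3. State in Section 11.0 that additional treatment will be summarised descriptively by arm, with medication and psychotherapy shown separately. Do not adjust the primary model for therapy begun after randomization.

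The cost is one or two REDCap items at three existing timepoints, under a minute of participant time at each, and a few sentences of protocol text.
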